- Explain that the purpose is to get them to a dose that causes clear, short-term improvement in PD symptoms during the next few weeks, but that has tolerable side effects (if any).
- Discuss possible benefit by reviewing their current typical PD motor symptoms.
- Discuss common side effects, including non-CNS (nausea, drop in blood pressure upon standing) and CNS (sleepiness, dyskinesias, rarely hallucinations) side effects.
- Give the patient a copy of the “Carbidopa-levodopa for Parkinson’s disease” handout.
- Ask them to keep track of any missed doses and of any observations or questions for us (e.g. on a 3x5 card or on a smart phone note).
- Confirm contact information and schedule a phone call within the next week.
- Give patients your and my contact information and encourage them to call with any concerns about the medication.

Start treatment with CD-LD 25/100mg tablets, one half tablet by mouth b.i.d. (morning and early afternoon).

Questions at each scheduled follow-up contact

- What symptoms are better?
- What symptoms are not?
- If not expressed spontaneously, inquire about each of these: tremor, stiffness, slowness, speech and gait
- If there is any benefit:
 - How long does it take to “kick in”?
 - How long does the benefit last?
- Any side effects?
- If not expressed spontaneously, inquire about the non-CNS and CNS side effects listed above.
- Are you satisfied with your treatment? Do you have any questions for me?
- (After 4 weeks) About how many tablets do you have left? [Enough until Scan Day 2?]

Dosing

1. If there is a CNS side effect other than mild, tolerable sleepiness, or for any questions, discuss with the PI.
2. Proceed based on the category below that best describes the patient’s current situation:
 - a. **Still has bothersome PD symptoms, no or minimal side effects:** If patient has been on current dose for less than 5 days, no change. If patient has been on current dose for at least 5 days, increase dose by one level (see dosing table below).
 - b. **Still has bothersome PD symptoms but also has non-CNS side effects:** If mild side effects and taking less than 100mg carbidopa per day, increase dose by one level. Otherwise add carbidopa 50mg p.o. q a.m., ½ hour before first CD-LD dose.

- c. **Still has bothersome PD symptoms but also has CNS side effects:** If patient had clear benefit at the previous dose, return to previous dose. Otherwise consult with PI.
- d. **Clear improvement and no remaining bothersome PD symptoms:** Continue drug at current dose schedule.

Dosing table for CD-LD 25-100mg tablets p.o.		
Level	Dose schedule	Total daily dose LD (mg)
1	0.5 tablets b.i.d.	100
2	0.5 tablets t.i.d. (morning, approximately noon, approximately 5pm)	150
3	
 ▪ if patient has had NO wearing off between b.i.d. doses: 1 tablet b.i.d.; ▪ if patient has had wearing off between b.i.d. doses: 1 tablet q a.m. plus 0.5 tablet at noon and at 5pm 	200
4	1 tablet t.i.d.	300
5	1.5 tablets t.i.d.	450
6	2 tablets t.i.d.	600
7	2.5 tablets t.i.d.	750

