9. An i.v. line is placed in each upper extremity (preferably antecubital; alternatively a hand vein), one for infusing levodopa solution and one for repeated blood samples. Saline lock. Usually the more affected side (by “off” tapping speed) will be connected to the small-bore light-resistant tubing for the levodopa infusion, and a clear extension tubing will be connected to the less affected side for later blood samples.
10. “Practical off” UPDRS Part III (motor exam)
11. Visual analog scales (VAS) to rate current affective state, PD symptoms and side effects (nausea/vomiting, sleepiness, dizziness or lightheadedness, and overall feeling poorly or well)
12. NIH Toolbox cognitive measures (approx. 17 minutes—see table above)
13. Blood sample for [LD] (baseline levodopa concentration)
14. Enter MRI room
 - a. Headphones or ear plugs are worn to dampen the noise of the scanner and for communication between the experimenter and subject.
 - b. Padding behind the head, thermoplastic mask, and/or nylon tape are used to restrict head movement.
 - c. Structural MRI scans (3D TSE and MPRAGE) before or after the ASL scans, or at least one hour after the start of the levodopa infusion
15. During the phMRI scans:
 - a. Ensure that at least 50 minutes have passed since carbidopa dose before starting ASL
 - b. ASL before i.v. levodopa for 10 minutes, subject fixating a crosshair
 - c. ASL during i.v. levodopa loading dose, subject fixating a crosshair
 - d. ASL repeatedly during maintenance levodopa infusion, subject fixating a crosshair
 - e. Breaks during the maintenance phase—preferably at least 30 minutes after start of LD infusion—as needed for subject comfort
 - f. Tapping speed with the more affected hand is repeated in the scanner using an MRI-compatible button device once during the pre-levodopa scan block, once within 1 minute of the end of the loading dose, and again within 2 minutes of the following times measured from the start of the loading dose: 0:20, 0:30, and every 15 minutes thereafter.

- g. Blood samples within 1 minute of 0:05:00, 0:10:30, 0:12:00, and 0:15:00, within 2 minutes of 0:19 and 0:24, and within 3 minutes of 0:30, 0:45, 1:00, 1:30.

16. After the MRI session:

- a. tapping speed with each hand separately (60 seconds sequentially depressing two keys 20cm apart with audible and tactile feedback; record the lower score of the 2 counters)

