- b. Tapping speed with the more affected hand (60 seconds sequentially depressing two keys 2cm apart with the index finger) using a device equivalent to an MRI-compatible button device.
- c. UPDRS part III
- d. Final blood sample
- e. Stop LD infusion
- f. VAS ratings
- g. Remove i.v. lines
- h. Record any benefit or side effect the patient noticed since the start of the infusion
- i. Provide a cab voucher if subject feels sleepy and had planned to drive home.

17. For Aim 2 subjects: Dispense supply of CD/LD tablets, confirm contact information, and confirm next study date.

Levodopa treatment between MR sessions (for subjects in Aim 2)

See “Treatments and Dosage,” a few pages below. This treatment is intended to match routine clinical practice. The initial treatment of PD varies among experts; CD/LD is a common option, and the most common one in the PI’s group practice, but other options include an MAO-A inhibitor, a dopamine agonist, or CD/LD combined with a COMT inhibitor. In other words, the 6-week initial treatment of Aim 2 subjects in this study is not off-label or experimental in the usual sense, but is standardized to a single treatment to reduce variability for the second pHMRI scan day.

With that exception, all procedures in this study are done for research purposes.

POTENTIAL RISKS

We have recently summarized the world literature on safety of i.v. levodopa and no SAEs are expected [16].

(The language below, in this section, is addressed to the patient, as in an informed consent document.)

You may experience one or more of the risks indicated below from being in this study. In addition to these, there may be other unknown risks, or risks that we did not anticipate, associated with being in this study. Some risks described in this consent document, if severe, may cause death. You will be told of any new information that may affect your willingness to participate in this study. [name] will answer any questions you have about these risks.

Levodopa

Likely:

- Temporary nausea
- Temporary sleepiness

Less likely:

- Temporary light-headedness (from lower blood pressure).
- Temporary vomiting
- Involuntary movements, hallucinations (seeing or hearing things that are not really there), delusions (being convinced of things that are objectively false), mental confusion, or impulse control disorders (like excessive gambling or change in sex drive). If any of these do occur, they are temporary.

Rare:

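### Three levodopa risks that the protocol names (delusions, confusion, impulse control disorders) have no specific question in the Aim 2 follow-up script

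*Combined protocol and SAP*

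**What the plan says.** Potential Risks, Levodopa, has one entry under Less likely that groups five effects: involuntary movements, hallucinations, "delusions (being convinced of things that are objectively false"), and "mental confusion, or impulse control disorders (like excessive gambling or change in sex drive").

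The appendix on dosing between scan visits has three relevant parts.

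- **Initiation of treatment.** Staff discuss non-CNS effects (nausea, a fall in blood pressure on standing) and "CNS (sleepiness, dyskinesias, rarely hallucinations) side effects".
- **Questions at each scheduled follow-up contact.** Staff ask "Any side effects"? and then: "If not expressed spontaneously, inquire about the non-CNS and CNS side effects listed above".
- **Dosing.** Rule 1 reads "If there is a CNS side effect other than mild, tolerable sleepiness, or for any questions, discuss with the PI". Rule 2a covers patients who still have bothersome symptoms and few or no side effects: "If patient has been on current dose for at least 5 days, increase dose by one level".

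Treatment lasts 6 ± 1 weeks (Study Design). Treatments and Dosage plans no dose change in the week before the second scan unless there is urgent clinical need.

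**The concern.** The script does not rely on the open question for the effects it lists: it asks openly and then requires a prompt for whatever was not volunteered. Delusions, confusion and impulse control changes get the open question but not the prompt.

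These are effects for which an open question is likely to do worst. A patient may not connect gambling or a change in sex drive with a Parkinson's tablet. By the protocol's own gloss, a person with a delusion is convinced of it, and so is unlikely to offer it as a side effect.

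The answers feed the dosing rules. A patient with one of these effects who does not mention it could be placed in the rule 2a category and moved up a level, and rule 1 would not be triggered. What is at stake is subject safety in a small group. The primary analysis is not affected.

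**Working it through.** The plan states no figure on this point, so the check is mainly a comparison of lists.

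**Step 1. Risk entry against prompts.**

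| Effect in the Less likely entry | In the list the follow-up prompt uses | Side-effect item on the scan-day VAS |
|---|---|---|
| Involuntary movements | Yes (as dyskinesias) | No |
| Hallucinations | Yes | No |
| Delusions | No | No |
| Mental confusion | No | No |
| Impulse control disorders | No | No |

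Of the five, 2 are prompted and 5 − 2 = 3 are not.

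**Step 2. Other routes by which the three could surface in Aim 2.**

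- The open question at each contact, and the closing question on satisfaction and queries: asked, but general.
- The patient's own notes and the invitation to call: these depend on the patient.
- MRI scan day item 3, the health-change notice to the PI: general. It applies again on scan day 2 because scan-day procedures are repeated.
- Item 16h, the record of benefits and side effects after scanning: covers only the period from infusion onset.
- Item 11, the VAS: scan days only. Besides affective state and PD symptoms it rates "side effects (nausea/vomiting, sleepiness, dizziness or lightheadedness, and overall feeling poorly or well").
- The neurological and psychiatric examination: listed at screening, before treatment.

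No route requires a specific question about any of the three during oral treatment.

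**Step 3. How far doses can move under rule 2a.** Daily levodopa is tablets per day × 100 mg. Recomputing the dosing table gives 100, 150, 200, 300, 450, 600 and 750 mg for levels 1 to 7, which matches it.

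The earliest day for level L under rule 2a is 5 × (L − 1). The last planned day for a change is 7 × weeks − 7.

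| Course | Last planned change | Highest level by rule 2a | Reached on day |
|---|---|---|---|
| 5 weeks | 35 − 7 = day 28 | 6 (600 mg/day) | 5 × 5 = 25 |
| 6 weeks | 42 − 7 = day 35 | 7 (750 mg/day) | 5 × 6 = 30 |
| 7 weeks | 49 − 7 = day 42 | 7 (750 mg/day) | 5 × 6 = 30 |

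This is the fastest path: a contact every 5 days, each ending in a rule 2a increase. Many subjects will stop lower. Rule 2b states no minimum time of its own, so the timetable describes rule 2a only.

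**Step 4. How many events to expect.** The documents give no incidence. If the per-subject risk p of an effect over the course is assumed to be 1%, 5% or 10%, the chance of at least one case in 10 subjects is 1 − (1 − p)^10 = 0.096, 0.401 or 0.651. Few events are expected, though the chance of at least one is not negligible over most of that assumed range.

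**The case against.** Much can be said for the plan. Staff do ask about side effects at every scheduled contact, patients keep notes and are encouraged to call, and the PI hears of health changes on scan day 2. The risk text is written for patients in consent style, so subjects should have been told of all three effects. Current psychosis, a primary psychotic disorder and MMSE below 24 are exclusions. NIH Toolbox tasks of attention, working memory, executive function and processing speed are repeated on scan day 2 and give some structured information on cognition. The appendix introduces its list as common effects and as examples, so staff are free to ask more. The oral treatment is meant to mirror ordinary practice.

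All of that stands, and it lowers the risk. It does not supply the missing prompt. The list is not confined to common effects, since it includes hallucinations as a rare one. The follow-up instruction refers to the effects listed, and nothing requires more. The Toolbox tasks come after titration and are not symptom questions.

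A reader might infer four stronger points that the documents do not support.

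- **That nobody asks at all.** The open question is put at each scheduled contact. What is missing is a specific question.
- **That doses rise for six weeks.** Increases depend on symptoms and tolerability, patients with clear improvement stay where they are, and the final week is a planned hold.
- **That a reported zero rate would reflect not asking.** No incidence estimate is planned. Adverse events go to the HRPO and into annual reports to the sponsor and the FDA.
- **That the VAS should have covered the oral-treatment period.** It rates current state around an infusion and was not designed for that.

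**Conclusion.** The gap is real and narrow. Three of the five effects in one risk entry have no targeted question during 5 to 7 weeks of oral treatment in 10 subjects, while rules 1 and 2a depend on such effects being known. Aligning the lists is a cheap improvement to safety ascertainment; no endpoint or analysis is at risk.

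The conclusion assumes that staff follow the script as written. The patient handout named in the appendix, and the remainder of the levodopa risk text, were not available for review and count neither way.

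**What to change.** Reconcile the appendix's CNS side-effect list with the Potential Risks section. Add delusions, confusion and impulse control changes (with the protocol's own examples of gambling and sex drive) in three places:

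1. the discussion at initiation of treatment;
2. the prompted questions at each scheduled follow-up contact;
3. the health-change check on scan day 2 for Aim 2 subjects.

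Rule 1 then applies to these effects as it stands. No dose, escalation rule or endpoint changes. The cost is a few words in the appendix, about a minute per contact, and possibly more minor reports to record.
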